4.6 Study Duration

Patients will receive treatment with BBI608 until progression of disease (clinical or radiological), unacceptable toxicity, or another discontinuation criterion is documented (see Section 5.7).

5 STUDY VISITS

5.1 Overview

Study Visits will consist of a Pre-Study Evaluation, during which the patient is evaluated to determine suitability for entry into the study; On-Treatment Evaluations, during which the patient is regularly evaluated during the conduct of the study; and an End-of-Study Evaluation (See APPENDIX A and APPENDIX B for schedules of Assessments).

Following the Pre-Study Evaluation and a determination by a Principal Investigator that the patient meets all inclusion/exclusion criteria, and after the patient signs the informed consent, the patient will be considered enrolled in the study.

In general, unless otherwise noted, a window of ± 2 days is allowed when scheduling protocol visits and evaluations. If, due to unforeseen circumstances, frame-shifting of a study cycle or patient visit schedule occurs beyond the allowable window of ± 2 days, the medical monitor for the Sponsor should be notified of the alternate schedule. The protocol window of ± 2 days may then be applied to the frame-shifted schedule.

Unscheduled clinical assessments during a study cycle are allowed, but should not replace a per-protocol study visit unless it is within the ± 2 day window.

5.2 Informed Consent

Patients who agree to participate will sign the approved informed consent and will be provided a copy of the signed document.

Informed consent may be obtained within approximately one month prior to the first dose of BBI608. All screening procedures (with exception of baseline MRI which should be performed within 28 days prior to enrollment) should be performed within 10 days of the first dose of BBI608 (unless otherwise noted).

5.3 Pre-Study Evaluations (Baseline)

After written informed consent is obtained according to ICH-GCP and local regulations, the patient will be evaluated for inclusion and exclusion criteria according to the eligibility criteria listed in Section 3.

The following will be evaluated and documented within 10 days prior to first dose of BBI608:

- Medical history
- Physical examination including a neurologic exam
- ECOG performance status score (see APPENDIX C)
- Vital signs (weight, temperature, blood pressure, height, respiration and pulse)
- Adverse Event assessment (from the date of informed consent)
- Assessment of concomitant medications from 28 days prior to the start of study treatment
- Hematology (see Section 6.3)
- Biochemistry (see Section 6.3)
- Urinalysis (see Section 6.3)
- Serum pregnancy test (if applicable)
- Archival tissue will be obtained as described in the Laboratory Manual once the patient has been enrolled.
- 12-lead electrocardiogram (ECG)
- Tumor measurement [magnetic resonance imaging (MRI) scan]*

* MRI scan performed within 28 days of the first scheduled dose of BBI608 can be used for baseline assessment if it was performed while off steroids or on a stable or decreasing steroid dosage for at least 5 days; otherwise, MRI should be performed within 14 days of dosing. This will be the baseline scan for patients in ARM B; repeat MRI obtained within 48-72 hours following surgery will be the baseline scan for the patients in ARM A for purposes of response assessment.

5.4 On-Study Assessments

5.4.1 Pre-Surgical BBI608 Monotherapy Run-in Phase (ARM A only)

These assessments will be performed ONLY for patients enrolled into Arm A of the study. Patients enrolled into Arm B of the study will start the study with the initiation of combination therapy with BBI608 and TMZ (section 5.4.3).

5.4.1.1 Run-in Week 1 (Day 1)

A Run-in Week 1, Day 1 visit should ONLY occur during the Pre-Surgical BBI608 Monotherapy Phase of the study and ONLY for patients enrolled into Arm A. Patients who meet all inclusion and exclusion criteria will have the following assessments:

- Vital signs (weight, temperature, blood pressure, respiration and pulse)
- Record concomitant medication
- Assess adverse events (AE)
- Dispense BBI608 (7 (\pm 2) day supply plus 2 extra days), please see the Pharmacy Manual for further information.

5.4.1.2 Run-in Week 2 (Day 8 - Day of Surgery)

A Run-in Day 8 visit should ONLY occur during the Pre-Surgical BBI608 Monotherapy Phase of the study and ONLY for patients enrolled into Arm A. Patients will have the following assessments:

- ECOG performance status score
- Vital signs (weight, temperature, blood pressure, respiration and pulse)
- Hematology (see Section 6.3)
- Biochemistry (see Section 6.3)
- Urinalysis (see Section 6.3)
- Assess adverse events (AE)
- Record concomitant medication including any changes in doses of corticosteroids

5.4.2 Surgical Resection of Recurrent GBM

ONLY patients enrolled into Arm A will undergo surgical resection of GBM.

BBI608 will be administered for 7 (\pm 2) days prior to a planned surgical resection of recurrent GBM. BBI608 will be administered on the morning of the surgical procedure (Run-in Week 2 Day 8) and BBI608 will remain held pending clinical post-operative recovery of the patient as determined by the investigator, for up to 28 days after surgery. Tumor sample will be obtained at time of surgical resection from T1/gadolinium enhanced lesion(s) as well as T2/FLAIR infiltrating tumor lesions and will be used to investigate BBI608 presence in the resected tumor tissue and will be used for pharmacodynamics analysis (please see the Laboratory Manual for additional information). Additionally, blood sample will be obtained at time of surgery to evaluate BBI608 pharmacokinetic (PK) exposure in the plasma (please see the Laboratory Manual for additional information). The time of BBI608 administration on the day of surgery and the collection times of blood sample will be recorded.

Tumor samples that are obtained at the time of surgical resection and are labeled with study protocol identification number and patient identification number will be sent to a regulatory authority-approved tumor bank affiliated with the study site, or to the study site pathology department if the site does not have a regulatory authority-approved tumor bank. In the event

that there is difficulty with establishment of histological diagnosis, tumor tissue will be made available to the pathology department at all study sites. Processing of all tumor tissue will include creation of both fresh frozen samples for PK analysis as well as blocks of formalin fixed paraffin-embedded (FFPE) samples for PD analysis.

An MRI will be performed 48-72 hours following surgery and will be used as the baseline scan for the purposes of tumor response evaluation in the patients who undergo surgical resection.

5.4.3 BBI608 Combination Therapy with Temozolomide

Following clinical post-operative recovery, Arm A patients will resume the study with this combination treatment phase. Patients enrolled into Arm B will begin the study directly at this phase.

5.4.3.1 Cycle 1 (Day 1)

Patients will have the following assessments:

- ECOG performance status score[^]
- Vital signs (weight, temperature, blood pressure, respiration and pulse)
- Physical examination including a neurologic exam[^]
- Serum pregnancy test (if applicable)- Arm A only
- 12-lead electrocardiogram (ECG)*
- Hematology (see Section 6.3)[^]
- Biochemistry (see Section 6.3)[^]
- Urinalysis (see Section 6.3)[^]
- Assess adverse events (AE)
- Record concomitant medication including any changes in doses of corticosteroids
- Dispense BBI608 (28 day supply plus 3 extra days), please see the Pharmacy Manual for further information
- Dispense TMZ **
- Blood samples for pharmacokinetics, red blood cell pellet Cycle 1 ONLY (please see the Laboratory Manual for further information)***

[^] For patients in Arm A only.

* The 12-lead electrocardiogram on Cycle 1 Day 1 should be obtained two hours *after* TMZ has been administered.

** A 3 hour interval between the first daily dose of BBI608 and the administration of TMZ is required on Days 1 and 5 of Cycle 1 only, in order to standardize PK interpretation. On all other days, the first daily administration of BBI608 can precede the administration of TMZ by 0-4 hours.

***Pharmacokinetics to be collected in Phase Ib/DLT assessment cohorts only

5.4.3.2 Cycle 1, Day 5

The patient will have the following assessments:

- ECOG performance status score
- Vital signs (weight, temperature, blood pressure, respiration and pulse)
- Assess adverse events (AE)
- Record concomitant medication including any changes in doses of corticosteroids
- Blood samples for pharmacokinetics, red blood cell pellet Cycle 1 ONLY (please see the Laboratory Manual for further information)***

** A 3 hour interval between the first daily dose of BBI608 and the administration of TMZ is required on Days 1 and 5 of Cycle 1 only, in order to standardize PK interpretation. On all other days, the first daily administration of BBI608 can precede the administration of TMZ by 0-4 hours.

***Pharmacokinetics to be collected in Phase Ib/DLT assessment cohorts only

5.4.3.3 Cycle 1 and Cycle 2 Day 8 (during Phase Ib)

The patient will have the following assessments:

- Hematology (see Section 6.3)
- Biochemistry (see Section 6.3)
- Urinalysis (see Section 6.3)

5.4.3.4 Cycle 1 and Cycle 2, Day 15

The patient will have the following assessments:

- ECOG performance status score
- Vital signs (weight, temperature, blood pressure, respiration and pulse)
- Hematology (see Section 6.3)
- Biochemistry (see Section 6.3)
- Urinalysis (see Section 6.3)
- Assess adverse events (AE)
- Record concomitant medication including any changes in doses of corticosteroids

5.4.3.5 Cycle 1 and Cycle 2 Day 22 (during Phase Ib)

The patient will have the following assessments:

- Hematology (see Section 6.3)
- Biochemistry (see Section 6.3)
- Urinalysis (see Section 6.3)

5.4.3.6 Cycle 2 and Beyond

Day 1

- Physical examination including a neurologic examination
- ECOG performance status score

- Vital signs (weight, temperature, blood pressure, respiration and pulse)
- Serum pregnancy test (if applicable)
- Hematology (see Section 6.3)
- Biochemistry (see Section 6.3)
- Urinalysis (see Section 6.3)
- Assess adverse events (AE)
- Record concomitant medication including any changes in doses of corticosteroids
- Dispense BBI608 (28 day supply plus 3 days), please see the Pharmacy Manual for further information
- Dispense TMZ

5.5 Tumor Evaluation Visits

For patients in Arm A, an MRI will be performed within 48-72 hours of surgery and will be used as the baseline exam for the purposes of tumor response evaluation in the patients who undergo surgical resection.

In both study arms, disease status and tumor response will be assessed at eight-week intervals until objective disease progression, or as clinically indicated, beginning approximately 8 weeks following initiation of combination therapy with BBI608 and TMZ. Standard imaging studies will be performed according to institutional procedures. Tumor response will be evaluated using the guidelines for Response Assessment in Neuro-Oncology (RANO) Working Group criteria outlined in **Section 9**, and study Case Report Forms (CRFs) will include relevant lesion measurements as determined by the study site. De-identified radiologic image dictation report as well as de-identified copies of the radiologic images for independent review may be requested in cases where radiologic assessment is in question.

Once clinical or radiological progression of disease during BBI608 therapy is documented, patients may continue treatment with BBI608 at the discretion of their treating physician.

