	
disease, or unacceptable toxicity, or until another discontinuation criterion is met. Treatment with BBI608 as monotherapy can continue if TMZ is discontinued for any reason. Also, the investigator may continue BBI608 in combination with TMZ or BBI608 monotherapy after the initial demonstration of radiological progression and in the absence of intolerable toxicities, performance status decline, worsening of disease related symptoms, radiographical findings that would warrant acute intervention and no ongoing severe toxicities that may be related to BBI608. The patient will also get repeat tumor assessments after 4-6 weeks. Treatment with BBI608 (with or without TMZ) will continue until unacceptable toxicity, further disease progression (clinical or radiological), or another discontinuation criterion is met.
 
Safety will be evaluated for the duration of the study. Adverse events will be documented using the current version of the NCI CTCAE (v 4.0).
										

Study Populations:
	
This study will enroll patients with histologically confirmed glioblastoma (GBM) at first recurrence of disease following front-line therapy.
 
Patients must have received prior treatment with standard first line therapy for GBM, including maximal surgical resection and postoperative external-beam radiotherapy. Concurrent chemoradiation with TMZ is allowed but not mandatory.
 
Patients are eligible for enrollment if they have unequivocal evidence of tumor recurrence/progression by MRI a minimum of 12 weeks following completion of radiation therapy or TMZ-Radiotherapy. Patients who have received prior bevacizumab or other anti-VEGF agents are not eligible to enroll.
 
Baseline MRI should be performed within 28 days prior to enrollment.
 
Other key inclusion criteria include ECOG status of 0-1 (KPS \geq 70%) and adequate bone marrow, hepatic, and renal function at baseline.
										

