
Duration of Treatment:
	
For an individual patient, treatment with BBI608 and TMZ will continue until unacceptable toxicity, disease progression (clinical or radiological), or another discontinuation criterion is met. Treatment with BBI608 as monotherapy can continue if TMZ is discontinued for any reason. Also, the investigator may continue BBI608 in combination with TMZ or BBI608 monotherapy after the initial demonstration of radiographic progression and in the absence of intolerable toxicities. The patient will also get repeat tumor assessments after 4-6 weeks. Treatment with BBI608 (with or without TMZ) will continue until unacceptable toxicity, further disease progression (clinical or radiological), or
										

	
another discontinuation criterion is met.

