5.7 Discontinuation from Study

Patients will be removed from the study at any time if they meet any of the following criteria:

- Documented radiologic or clinical progression of disease

- Noncompliance with any part of the study, as evaluated by the Principal Investigator and Medical Monitor
- Withdrawal of consent
- Investigator decision
- Lost to Follow-up
- Death
- Clinically unacceptable toxicities despite optimal treatment or dose reduction
- Pregnancy

*RANO criteria serve to categorize clinical radiologic images. Given a unique mechanism of action targeting cancer stem cells, BBI608 therapy may be continued in a patient who is clinically well, but who meets criteria for “Progressed Disease” per RANO criteria. Continuation of BBI608 protocol therapy in this context is allowed provided no further standard, approved treatment options exist; and provided the investigator assess that the potential benefit to the patient outweighs the potential risk and in the absence of intolerable toxicities, performance status decline, worsening of disease related symptoms, radiological findings that would warrant acute intervention and no ongoing severe toxicities that may be related to BBI608. The patient will also get repeat tumor assessments after 4-6 weeks. Treatment with BBI608 (with or without TMZ) will continue until unacceptable toxicity, further disease progression (clinical or radiological), or another discontinuation criterion is met.

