Patients will continue treatment with BBI608 and TMZ until the investigator has determined that they are no longer clinically benefiting due to progression of disease, or unacceptable toxicity, or until another discontinuation criterion is met. Treatment with BBI608 as monotherapy can continue if TMZ is discontinued for any reason. Also, the investigator may continue BBI608 in combination with TMZ or BBI608 monotherapy after the initial demonstration of radiological progression and in the absence of intolerable toxicities, performance status decline, worsening of disease related symptoms, radiographical findings that would warrant acute intervention and no ongoing severe toxicities that may be related to BBI608. The patient will also get repeat tumor assessments after 4-6 weeks.

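### Protocol 5.5 lets BBI608 continue after clinical progression at the physician's discretion, whereas 5.7 removes such patients and allows continuation only under conditions that 5.5 and the synopsis drop wholly or in part

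*Protocol*

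**What the plan says.** Five places allow BBI608 to go on after progression.

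- **Protocol 5.5 (Tumor Evaluation Visits):** "Once clinical or radiological progression of disease during BBI608 therapy is documented, patients may continue treatment with BBI608 at the discretion of their treating physician". Nothing else is required, and 5.7 is not mentioned.
- **Protocol 5.7 (Discontinuation from Study):** the first criterion for removal is "Documented radiologic or clinical progression of disease". An asterisked note under the list then says that "BBI608 therapy may be continued in a patient who is clinically well" although RANO progression is met, and adds: "Continuation of BBI608 protocol therapy in this context is allowed provided no further standard, approved treatment options exist". The note also asks for the investigator's judgement that benefit outweighs risk. It rules out intolerable toxicity, declining performance status, worsening symptoms, imaging findings that need acute intervention, and ongoing severe toxicity. Tumor assessment is repeated after 4-6 weeks.
- **Protocol synopsis, Study Design:** "the investigator may continue BBI608 in combination with TMZ or BBI608 monotherapy after the initial demonstration of radiological progression", subject to the toxicity, performance status, symptom and imaging conditions, with the 4-6 week repeat assessment.
- **Protocol synopsis, Duration of Treatment:** continuation "after the initial demonstration of radiographic progression and in the absence of intolerable toxicities", with the repeat assessment but none of the other conditions.
- **SAP 2.1:** continuation "after the initial demonstration of radiological progression and in the absence of intolerable toxicities, performance status decline, worsening of disease related symptoms", with the same further conditions as the synopsis Study Design row.

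Protocol 4.6 states the ordinary stopping rule ("Patients will receive treatment with BBI608 until progression of disease (clinical or radiological), unacceptable toxicity") and refers the reader to Section 5.7.

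**The concern.** The protocol gives two answers to one question: must the investigational drug stop when a patient progresses clinically? Section 5.7 says yes and 5.5 says not necessarily. Nothing in either document says which section prevails.

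The restriction in 5.7 has a purpose. RANO progression in Protocol 9.3 includes clear clinical deterioration caused by the tumor, so meeting RANO progression does not by itself separate a well patient with a worse scan from a patient who is failing. In 5.7 the requirement to be clinically well, with the performance status and symptom conditions, makes that separation. Section 5.5 has none of these.

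What is at stake is mainly patient protection and length of exposure: a deteriorating patient could be kept on an unproven drug, or a patient could stay on it while a standard option is still open. There may also be a consequence for how progression is ascertained.

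**Working it through.** No sample-size or power figure is involved. The check is a comparison of the five continuation statements.

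| Element | 5.5 | 5.7 note | Synopsis, Study Design | Synopsis, Duration | SAP 2.1 |
|---|---|---|---|---|---|
| Covers clinical progression | yes | no | no | no | no |
| No intolerable toxicity | not stated | required | required | required | required |
| No performance status decline or symptom worsening | not stated | required | required | not stated | required |
| No imaging finding needing acute intervention; no ongoing severe toxicity | not stated | required | required | not stated | required |
| No standard, approved option left | not stated | required | not stated | not stated | not stated |
| Repeat assessment after 4-6 weeks | not stated | required | required | required | required |

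**Counts.** One of five statements (5.5) reaches clinical progression. One of five (5.7) carries the no-standard-option condition, so 5 - 1 = 4 lack it. One of those four is 5.5 itself, so besides 5.5 and 5.7 the condition is missing from 4 - 1 = 3 places: the two synopsis rows and SAP 2.1.

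**Can 5.5 and 5.7 be reconciled?** Take a patient with documented clinical progression. Under 5.7 the patient meets a removal criterion and, not being clinically well, falls outside the exception. Under 5.5 the patient may continue if the treating physician chooses. Reading 5.5 as shorthand for 5.7 fails, because 5.5 names clinical progression expressly and does not point to 5.7.

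**Does the choice reach the primary endpoint?** It could.

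1. SAP Appendix 1.2, Table 4, note 1 does not count symptomatic deterioration without radiographic confirmation as progression.
2. Table 4 censors a patient who starts new anticancer treatment without tumor progression, at the last adequate scan before that treatment (or at first dose, if later).
3. A clinically progressed patient kept on BBI608 under 5.5 may go on being scanned, and a later radiographic progression could count as an event.
4. The same patient removed under 5.7 has only passive imaging follow-up (Protocol 5.6) and may be censored on switching therapy.
5. SAP 8.2.2.2 estimates PFS-6 by Kaplan-Meier, so event or censored status enters the estimate.

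The documents do not say how many patients would follow either path, so no size can be given.

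**How much does the no-standard-option condition restrict?** Protocol 1.2 names temozolomide and bevacizumab among the limited options at recurrence, and Protocol 3.2 excludes prior bevacizumab or other anti-VEGF treatment. If bevacizumab counts as standard and approved for the purpose of 5.7, the condition could bar many continuations that the other four places allow. Section 1.2 also says that standard second-line recommendations are lacking, which points the other way. The documents do not settle it.

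**The case against.** The strongest reply is that 5.7 is the detailed rule and the other places are summaries. Leaving one condition out of a synopsis row or a SAP design paragraph is incompleteness rather than contradiction, and the synopsis Study Design row and SAP 2.1 already carry most of the safety conditions. Much of this stands. It does not rescue 5.5, which is in the protocol body and positively permits what 5.7 excludes. Nor does it fully answer for the Duration of Treatment row, which keeps one safety condition and drops the rest.

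Four stronger readings are tempting and should not be made.

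- A reader might infer that 4.6 and the progression bullet in 5.7 also contradict the exception. They do not: 4.6 refers to Section 5.7, and the asterisked note directly below the list serves as the exception to that bullet. The asterisk's anchor is not visible in the extracted text, which may be a conversion loss.
- A reader might infer that sites would treat patients from SAP 2.1. Sites work from the protocol, so the SAP mismatch is housekeeping.
- A reader might infer that PFS-6 is safe because RANO progression counts whether or not treatment continues. For clinical progression without radiographic confirmation, Table 4 note 1 says otherwise. The opposite inference, that PFS-6 is biased by a known amount or in a known direction, is equally unsupported.
- A reader might infer that 5.7 must be the intended rule in every detail. The documents do not say so, and the no-standard-option condition in particular needs the sponsor's confirmation.

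**Conclusion.** The point holds as a conflict between Protocol 5.5 and 5.7 over continuation after clinical progression, with a lesser misalignment in the synopsis (chiefly the Duration of Treatment row) and a minor one in SAP 2.1. It rests on the wording alone. It assumes only that a site could act on 5.5 as written. The consequence is for patient protection and exposure. The sample size and its precision statement are untouched. An effect on PFS-6 is possible through event status, but neither its size nor its direction can be derived. It should be corrected, and the correction is small.

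**What to change.** 1. Replace the continuation sentence in Protocol 5.5 with: *After radiological progression BBI608 may continue only if all conditions in Section 5.7 are met; it stops at clinical progression.*
2. Make the continuation sentence in the synopsis Duration of Treatment row refer to Section 5.7, and do the same in the Study Design row for consistency.
3. Match SAP 2.1 as housekeeping.
4. Before making these edits, have the sponsor confirm whether the condition that no standard, approved option remains is intended for this trial, and state in 5.7 whether bevacizumab counts as such an option. If the condition is not intended, remove it from 5.7 rather than spreading it by cross-reference.

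No edit to 4.6 or to the progression bullet in 5.7 is needed.

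The cost is three sentences in the protocol and one in the SAP, with the IRB approval that Protocol 13.1 requires for a protocol change. Sample size and analysis stay as they are. The real downside lies in step 4: in a population without prior bevacizumab, a confirmed condition could bar many continuations. SAP 8.1.1 records that the sponsor ended all follow-up after 29JUN2018. If the edits come too late to guide treatment, the study report should state which rule sites applied and list patients treated past progression, marked as clinical or radiological.
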